Time to change of concomitant AD treatment will be analyzed similarly to that for time to conversion to dementia based on clinical diagnosis. Time to change of concomitant AD treatment is defined as time from randomization to the first dose increase and/or initiation of treatment with AChEI or memantine after randomization. For subjects without any change of concomitant AD treatment by the end of study, the time to change of concomitant AD treatment will be censored at the date of last assessment of concomitant medication.

The proportion of subjects with any change of concomitant AD treatment at 24 months will be analyzed similarly to that for proportion of subjects with dementia diagnosis at 24 months.

The rate of change over time (mean slope) based on change from baseline in the NPI-10 item will be analyzed in a manner similar to that used for the rate of change over time (mean slope) based on change from baseline in the CDR-SB.

The analysis of the following exploratory efficacy endpoints will be performed to compare elenbecestat versus placebo using the appropriate prespecified statistical methods including MMRM model, analysis of covariance model (ANCOVA), etc. For each exploratory efficacy endpoint, the treatment effect for elenbecestat 50 mg per day versus placebo will be tested at a significance level of 2-sided $\alpha = 0.05$.

- Change from baseline in NPI-10 item at 24 months
- Change from baseline in EQ-5D (subject self-reported, study partner self-reported, and subject measured by proxy) and QOL-AD (subject and study partner) at 24 months
- Change from baseline in Zarit's Burden Interview at 24 months

Additional analyses may be performed as needed.

Pharmacokinetic, Pharmacodynamic, Pharmacogenomic, and Other Biomarker Analyses

Pharmacokinetics

Safety Analysis sets will be used for individual elenbecestat plasma and CSF concentration listings. The PK Analysis Set will be used for the summaries of elenbecestat plasma and CSF concentrations.

A population PK approach will be used to characterize the PK of elenbecestat. The effect of covariates (ie, demographics) on elenbecestat PK will be evaluated. The PK model will be parameterized for clearance (CL) and volumes of distribution. Derived exposure parameters such as area under the concentration \times time curve (AUC) will be calculated from the model using the individual posterior estimate of CL and dosing history.

Pharmacokinetic-Pharmacodynamic

The PK/PD relationship between CSF biomarker levels and plasma PK parameters or CSF concentrations of elenbecestat will be explored graphically and any emergent relationship will be explored through population PK/PD modeling. These PK parameters include maximum observed concentration (C_{max}), and $AUC_{(0-24)}$ derived from the population PK model. The PK/PD relationship between plasma PK parameters and CSF concentrations of elenbecestat with other biomarkers may also be explored using similar methods.

Additionally, the relationship between various PK parameters (eg, C_{max}) or CSF concentrations of elenbecestat and CDR-SB at 24 months, and the relationship between various PK exposure

parameters or CSF concentrations of elenbecestat and the change from Baseline for 24 months in ADAS-cog14, and the MMSE, will be explored graphically. Any emergent relationships will be explored through population PK/PD modeling. The relationship between exposure to elenbecestat and most frequent AEs will also be explored.

Safety Analyses

Evaluations of safety will be performed on the Safety Analysis Set. The incidence of AEs, out-of-normal-range laboratory safety test variables, abnormal ECG findings, and out-of-range vital signs, suicidality, events of possible signals of drug abuse potential, along with change from baseline in laboratory safety test variables, ECGs, and vital sign measurements will be summarized by treatment group. (revised per Amendment 05)

Other Analyses

MRI (including vMRI and fMRI) sequences will be collected for all subjects at 12 and 24 months per the Schedule of Assessments. vMRI data will be analyzed at the Screening Visit and at Visits 9 and 13 (12 and 24 months of treatment). QC and normalization procedures for measurements of the whole brain, total ventricular volume, and right and left hippocampal volumes will be based on a validated algorithm and conducted in the same central laboratory. Additional analysis of regions of interest and cortical thickness may also be performed.

Extension Phase (revised per Amendment 05)

Primary Endpoint

- Safety endpoints: AE, vital sign, ECG, physical examination, neurological examination, laboratory safety test, suicidality assessment, events of possible signals of drug abuse potential, and MRI safety parameters

Secondary Endpoints

- Changes from Core Study baseline in CDR-SB, ADCOMS, MMSE, FAQ, ADAS-cog14, and ADAS-cog14 Word List (immediate recall and delayed recall)
- Time to conversion to dementia for subjects who were not clinically staged as dementia at Core Study baseline based on clinical diagnosis

Biomarker Endpoints

- Changes from Core Study baseline in:
 - Brain amyloid and tau PET levels
 - Total hippocampal volume as measured by vMRI
 - fMRI parameters as appropriate
 - CSF t-tau, p-tau and amyloid beta ($A\beta(1-42)$) levels
 - Plasma and CSF amyloid beta ($A\beta(1-x)$)
 - CSF biomarkers of AD (eg, NFL, VILIP1, YKL-40, and Ng)
 - Blood biomarkers of AD (eg, NFL, VILIP1, YKL-40)

Exploratory Endpoints

- Changes from Core Study baseline in NPI-10 and if available NPI-12
- Proportion of subjects who receive increase and/or initiation of other AD pharmacotherapies

Extension Phase Analysis Sets

The analysis sets defined in the Core Study will also be used for the analyses in the Extension Phase,

which include: Safety, FAS, PPS and PD Analysis Set.

Safety Analyses

Safety analysis will be performed similarly to analyses in the Core Study. The Core Study baseline will be used for subjects who are randomized to elenbecestat initially, the Extension Phase baseline will be used for subjects who are randomized to placebo but receive elenbecestat during the Extension phase. The incidence of AEs (including changes from baseline in physical and neurological examinations, and dermatological assessments), out-of-normal-range laboratory safety test variables, abnormal ECG findings, out-of-range vital signs, suicidality (C-SSRS), and changes from baseline in laboratory safety test variables, ECGs, safety MRI, vital sign measurements will be summarized by using descriptive statistics.

Efficacy Analyses

The following efficacy endpoints will be summarized by descriptive statistics and graphs:

- Changes from baseline in CDR-SB, ADCOMS, MMSE, FAQ, ADAS-cog14, and ADAS-cog14 Word List (immediate recall and delayed recall)
- Time to conversion to dementia for subjects who were not clinically staged as dementia at Core Study baseline based on clinical diagnosis
- Change from baseline in NPI-10 and NPI-12
- Proportion of subjects who receive an increase and/or initiation of other AD pharmacotherapies

A delayed-start analysis ([Liu-Seifert et al, 2015](#)) will be performed for each efficacy endpoint at various scheduled visits in the Extension Phase. In addition, the MMRM model will be used to analyze the above endpoints where appropriate.

Biomarker Analyses

The following biomarker endpoints will be summarized by descriptive statistics and graphs:

- Change from baseline in amyloid PET SUVR
- Change from baseline in tau PET signal
- Change from baseline in total hippocampal volume as measured by vMRI
- Change from baseline in the preservation of connectivity as measured by fMRI
- Change from baseline in t-tau, p-tau, A β (1-42) and A β (1-x) in CSF
- Change from baseline in A β (1-x) in plasma
- Change from baseline in exploratory biomarkers eg, NFL, VILIP1, YKL-40, and Ng in CSF and plasma

A delayed-start analysis and MMRM model will be used to analyze these biomarker endpoints. The relationship between efficacy endpoints and biomarker endpoints will be explored using correlation analysis.

Interim Analyses

This is a fixed design. There is no interim analysis of efficacy and no alpha spending before final analysis. However, a futility analysis is planned when approximately 30% subjects in the combined

2 studies (E2609-G000-301 and E2609-G000-302) have had an opportunity to complete the 24-month visit of the Core Study by the interim cutoff date. The sponsor may stop the trial for futility with nonbinding futility boundary calculated using conservative O'Brien-Fleming boundary of Lan-DeMets alpha spending function with 30% information based on completers. If the actual percent information of the futility analysis is different from 30%, the futility boundary will be recalculated using the actual percent information at the time of the futility analysis. A blinded sample size re-estimation through estimated standard deviation based on blinded data before the completion of enrollment, will be performed if there is an indication that sample size assumptions need to be changed. This blinded sample size re-estimation could be performed based on signals from external studies or based on review of blinded data from this study before completion of enrollment. The standard deviation of the primary endpoint was originally estimated based on data from the ADNI study. It is possible that the standard deviation for the same endpoint in clinical trials may be larger than that from this observational study. (revised per Amendment 05)

Sample Size Rationale

The sample size for this study is estimated for comparison of elenbecestat versus placebo with respect to a pooled analysis of studies E2609-G000-301 and E2609-G000-302 for the change from baseline in CDR-SB at 24 months. Based on the available data from the placebo group in Study BAN2401-G000-201 (a recently completed study with a comparable subject population), the mean and the standard deviation of the change from baseline in CDR-SB at 24 months in the placebo group are assumed to be 1.46 and 2.05, respectively, instead of 1.75 and 2.05, which are originally assumed by the available data from ADNI (of amyloid positive, MMSE equal or greater than 24, late MCI [global CDR=0.5, CDR memory box \geq 0.5]) is selected to estimate the mean and standard deviation of the change from baseline in CDR-SB at 24 months in the placebo group, which are 1.5 and 2.05, respectively. Therefore, assuming a 25% reduction in the mean change from baseline CDR-SB at 24 months for elenbecestat compared to placebo with common standard deviation of 2.05 and 30% dropout rate, a total sample size of 1900 subjects, 950 subjects in each treatment group, will be required to detect the treatment difference between elenbecestat and placebo using a 2-sample t test with 90% power at a significance level of 2 sided alpha =0.05.

The pooled data from 2 studies (E2609-G000-301 and E2609-G000-302) will comprise the total sample size of approximately 1900 subjects. At least 850 subjects will be randomized in each study. (revised per Amendment 05)

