9.3.3 Removal of Subjects from Therapy or Assessment

The investigator may withdraw the subject from the study at any time for safety or administrative reasons. The subject may stop study drug or withdraw from the study at any time for any reason.

Absolute lymphocyte count from the hematology and differential panel will be monitored during the study. Should a subject develop a Grade 2 or greater lymphocytopenia (less than $800/\text{mm}^3$), this should be confirmed as soon as possible but no later than within 5 days with a repeat test of absolute lymphocyte count. If confirmed, study drug administration should be interrupted for a minimum period of 2 weeks and for a maximum period of 4 weeks. Restart of study drug may take place only when absolute lymphocyte count returns to greater than LLN. Absolute lymphocyte count will be measured 4 weeks after restart of study drug. Subsequent measurements of absolute lymphocyte counts will follow the schedule of assessments (Table 3) and any results showing a Grade 2 or greater lymphocytopenia (less than $800/\text{mm}^3$) should be handled as above. If a 2nd occurrence of Grade 2 or greater lymphocytopenia (less than $800/\text{mm}^3$), that is confirmed on repeat testing, occurs within 6 months, then the subject should be discontinued permanently from the study drug. (revised per Amendment 01)

Subjects who discontinue study drug early must complete the ED Visit (within 7 days of the last dose of study drug) and the Follow-Up Visits (1 and 3 months after the last dose of study drug). These Follow-Up Visits will be conducted to monitor efficacy and safety parameters after early withdrawal from the study or discontinuation of study drug.

All subjects who discontinue study drug before reaching 12 months of treatment will also be asked to return to the clinic for a 12-month clinical assessment and then again at 24 months. Subjects who discontinue treatment between 12 and 24 months of treatment will be asked to return to the clinic for a 24 month clinical assessment. Subjects who discontinue early from study drug are considered “on study” as long as they continue to return for their regularly scheduled clinical assessments at 12 and 24 months as outlined above, at which efficacy and quality of life will be assessed along with concomitant medications and AEs. However, subjects who discontinue study drug early are not considered to have ‘completed’ the study as a final Subject Disposition.

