9.5.4.1 Reporting of Serious Adverse Events

All SAEs, regardless of their relationship to study treatment, must be reported on a completed SAE form by email or fax as soon as possible but no later than 24 hours from when the investigator becomes aware of the event.

SAEs, regardless of causality assessment, must be collected up to 12 weeks after the last dose of study drug. All SAEs must be followed to resolution or, if resolution is unlikely, to stabilization. Any SAE judged by the investigator to be related to the study treatment or any protocol-required procedure should be reported to the sponsor regardless of the length of time that has passed since study completion.

The detailed contact information for reporting of SAEs is provided in the Investigator Study File.

For urgent safety issues, please ensure all appropriate medical care is administered to the subject and contact the appropriate study team member listed in the Investigator Study File.

It is very important that the SAE report form be filled out as completely as possible at the time of the initial report. This includes the investigator's assessment of causality.

Any follow-up information received on SAEs should be forwarded within 1 business day of its receipt. If the follow-up information changes the investigator's assessment of causality, this should also be noted on the follow-up SAE form.

Preliminary SAE reports should be followed as soon as possible by detailed descriptions including copies of hospital case reports, autopsy reports, and other documents requested by the sponsor.

The investigator must notify his/her IRB/IEC of the occurrence of the SAE in writing, if required by their institution. A copy of this communication must be forwarded to the sponsor, or its designee, to be filed in the sponsor's Trial Master File.

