In some cases, unscheduled (UNS) visits will be needed to follow-up on safety or other findings, and the related assessments (outlined in the Schedule of Assessments) will depend on the reason for the UNS visit, and will be decided at the discretion of the investigator.

For subjects who consent to the Amyloid PET longitudinal substudy, Amyloid PET will be conducted after 12 and 24 months of treatment during the Core Study (or at the ED visit, provided the subject

has received at least 39 weeks of study drug). For subjects who consent to the CSF longitudinal substudy, CSF will be collected after 24 months of treatment (or at the ED visit, provided the subject has received at least 39 weeks of study drug).

Safety assessments including physical examinations with dermatologic review by the study investigator, neurologic exams, assessments of suicidal thinking and behavior, standard laboratory assessments, and ECGs, and blood assessment for PK will be performed throughout the 24 months of treatment in the study.

Subjects who discontinue study drug early must complete the ED Visit (within 7 days of the last dose of study drug) and the Follow-Up Visits (1 and 3 months after the last dose of study drug). These Follow-Up Visits will be conducted to monitor efficacy and safety parameters after early withdrawal from the study or discontinuation of study drug.

All subjects who discontinue study drug before reaching 12 months of treatment during the Core Study will also be asked to return to the clinic for a 12-month clinical assessment and then again at 24 months. Subjects who discontinue treatment between 12 and 24 months of treatment will be asked to return to the clinic for a 24 month clinical assessment. Subjects who discontinue early from study drug are considered “on study” as long as they continue to return for their clinical assessments at 12 and 24 months as outlined above, at which efficacy and quality of life will be assessed along with concomitant medications and AEs. However, subjects who discontinue study drug early are not considered to have ‘completed’ the study as a final Subject Disposition.

Data Safety Monitoring Board

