Subjects who discontinue study drug early must complete the ED Visit (within 7 days of the last dose of study drug) and the Follow-up Visits (1 and 3 months after the last dose of study drug). These Follow-up Visits will be conducted to monitor efficacy and safety parameters after early withdrawal from the study or discontinuation of study drug.

All subjects in the Core Study who discontinue study drug before reaching 12 months of treatment during the Core Study will also be asked to return to the clinic for a 12-month clinical assessment and then again at 24 months. Subjects who discontinue treatment between 12 and 24 months of treatment will be asked to return to the clinic for a 24-month clinical assessment. Subjects who discontinue early from study drug are considered “on study” as long as they continue to return for their clinical assessments at 12 and 24 months as outlined above, at which efficacy and quality of life will be assessed along with concomitant medications. New AEs will be collected for 4 weeks post last dose and followed-up for 12 weeks, or until resolution, whichever comes first. AEs relating to study procedures will be collected until the end of study participation. (revised per Amendment 05) However, subjects who discontinue study drug early are not considered to have ‘completed’ the study as a final Subject Disposition.

Data Safety Monitoring Board

An independent Data Safety Monitoring Board (DSMB) will convene at regular intervals to monitor the overall safety of the study and to make recommendations to the sponsor related to study safety as appropriate. The DSMB will be asked to review the cumulative safety data, which includes measures of cognitive safety at the group level, up to the date identified to make a determination if the trial is safe to proceed unchanged or to provide recommendations to the sponsor as to how to proceed. The study will proceed, including randomization of additional subjects, during DSMB safety reviews. Details will be provided in the DSMB Charter. (revised per Amendment 05)

Extension Phase

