- The PD Analysis Set is the group of subjects who have sufficient PD data to derive at least 1 PD parameter.

Efficacy Analyses

The FAS will be used as the primary population for all efficacy analyses, while the PPS will be used as the supportive population.

Analyses for Primary Efficacy Endpoints

The primary analysis will be based on an intent to treat philosophy without regard to adherence to treatment. The primary analysis of the change from baseline in CDR-SB at 24 months will be performed to compare elenbecestat 50 mg per day versus placebo using a linear mixed effects model for repeated measures (MMRM) on the FAS. The MMRM model will include fixed effects of treatment group, visit, treatment group by visit interaction, baseline CDR-SB, baseline CDR-SB by visit interaction, and randomization stratification variables (ie, region [7 levels], clinical dementia [yes, no], and concurrent AD medication use at randomization (Visit 2) [yes, no]). *ApoE4* status may be included in the model if appropriate. (revised per Amendment 05) An unstructured covariance matrix will be employed to model the covariance of within subject effect; if MMRM fails to converge then a covariance structure with fewer parameters from the following list will be employed according to the prespecified order in the list until the MMRM converges. The list of covariance structure will include Heterogeneous Toeplitz, Toeplitz, Heterogeneous Compound Symmetry, and Compound Symmetry. This primary analysis will include all observed post baseline data of the change from

baseline in CDR-SB without imputation of missing values. The treatment effect for elenbecestat versus placebo will be compared at 24 months based on MMRM model. The LS means and difference in LS means between elenbecestat treatment group and placebo, and corresponding 95% confidence interval (CI) will be presented.

The null hypothesis is that there is no difference in the mean change from baseline in CDR-SB at 24 months between elenbecestat 50 mg per day and placebo. The corresponding alternative hypothesis is that there is a difference in the mean change from baseline in CDR-SB at 24 months between elenbecestat 50 mg per day and placebo.

The primary analysis will be repeated to minimize the impact of change in concomitant AD medications where efficacy data after initiation of new AD medications and increase of current AD medications will be censored.

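### New adverse events are collected only to 4 weeks after the last dose in subjects who stop drug but stay on study, so the harm comparison by arm stops short of month 24 while efficacy does not

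*Protocol*

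**What the plan says.** The Version 7.0 synopsis (Core Study) treats subjects who discontinue drug early as still on study if they attend later assessments. Those who stop before month 12 are asked back at months 12 and 24. For later stoppers: "Subjects who discontinue treatment between 12 and 24 months of treatment will be asked to return to the clinic for a 24-month clinical assessment". The content of these visits is given as "at which efficacy and quality of life will be assessed along with concomitant medications"; adverse events are not listed there. The collection rule follows: "New AEs will be collected for 4 weeks post last dose and followed-up for 12 weeks, or until resolution, whichever comes first". The one stated exception is "AEs relating to study procedures will be collected until the end of study participation".

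On efficacy, the same synopsis states: "The primary analysis will be based on an intent to treat philosophy without regard to adherence to treatment". Safety is summarised by treatment group on the Safety Analysis Set.

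The Version 7.0 synopsis says in general terms that all adverse events and SAEs are recorded, but it sets no window for SAEs or deaths. In the earlier protocol text supplied, Section 9.5.4.1 has "SAEs, regardless of causality assessment, must be collected up to 12 weeks after the last dose of study drug", and adds that SAEs judged related to treatment or to a protocol procedure are reportable however long after the study. That earlier text also described the return visits differently (Section 9.3.3): "at which efficacy and quality of life will be assessed along with concomitant medications and AEs".

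**The concern.** A benefit-risk comparison is easiest to read when benefit and harm are counted over the same people and the same time. Here the month-24 CDR-SB of a subject who stopped drug at month 6 counts in that subject's randomised arm. A non-procedural event that began at month 9 in the same subject has no stated route into the database.

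The loss need not be equal between arms. The Version 7.0 synopsis requires permanent discontinuation after two confirmed Grade 2 or worse lymphocytopenias within 6 months, and the Introduction (Section 7.1, earlier text) reports some CD4 reduction at 50 to 100 mg. If more subjects stop on elenbecestat, that arm loses more safety observation, and part of the loss falls on subjects taken off drug for a safety reason. This is plausible rather than shown: no discontinuation rate by arm is given.

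The gap comes from the wording of the rule. The return visits are already scheduled.

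**Working it through.** **Inputs**
- Pooled sample size 1900 (950 per arm), 25% reduction, SD 2.05, 30% dropout, 90% power, two-sided 5%: Version 7.0 synopsis, Sample Size Rationale.
- Treatment period 24 months, placed at 104 weeks in the visit schedule (earlier text).
- Collection window for new adverse events, w = 4 weeks = 4 × 24/104 = 0.92 months: Version 7.0 synopsis.
- SAE window, w = 12 weeks = 12 × 24/104 = 2.77 months: Section 9.5.4.1, earlier text.
- Share of subjects who stop drug and stay on study: not given. Assumed 5% to 30%.
- Stopping time: assumed uniform over 0 to 24 months.

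**The plan's own figure, to see what the 30% means.** With a placebo mean of 1.46, the difference is 0.25 × 1.46 = 0.365. Then n per arm = 2 × (1.960 + 1.282)² × 2.05² / 0.365² = 663. Dividing by 0.7 gives 948 per arm, 1896 in total, against 1900 stated. The 30% is therefore an allowance for subjects who supply no month-24 value. It does not count those who stop drug and still attend, so it serves here only as an assumed upper end.

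**Single subjects.** Months without collection before month 24 = 24 − stopping month − w.

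| Drug stopped at | New adverse events (4 weeks) | Unrelated SAEs (12 weeks) |
|---|---|---|
| Month 6 | 17.1 | 15.2 |
| Month 12 | 11.1 | 9.2 |
| Month 18 | 5.1 | 3.2 |

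**Average per discontinuer.** For uniform stopping times the mean is (24 − w)² / 48.
- 4 weeks: (24 − 0.92)² / 48 = 11.09 months.
- 12 weeks: (24 − 2.77)² / 48 = 9.39 months.

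**Whole trial.** Planned subject-months = 1900 × 24 = 45,600.

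| Share who stop and stay | Subjects | No new-event collection (4 weeks) | No unrelated-SAE collection (12 weeks) |
|---|---|---|---|
| 5% | 95 | 1,054 (2.3%) | 892 (2.0%) |
| 10% | 190 | 2,108 (4.6%) | 1,784 (3.9%) |
| 20% | 380 | 4,216 (9.2%) | 3,568 (7.8%) |
| 30% | 570 | 6,324 (13.9%) | 5,353 (11.7%) |

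The percentages equal share × mean / 24, so they are the same for one study or for the pooled pair. No power or sample-size figure changes.

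**The case against.** The quoted rule concerns new adverse events. A reader might infer that deaths and serious harm are not compared by arm at all. The documents do not support that. Safety is summarised by treatment group, the Version 7.0 synopsis sets no SAE or death cut-off, and the SAE rule that can be seen runs to 12 weeks, with no limit for related SAEs. The amendment history says that Sections 9.3.3 and 9.5.1.5.1 were revised on exactly this group of subjects, and those revised sections are not among the pages supplied. The comparison is cut off in time; it is not absent, and its SAE and death part is probable rather than proven.

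A reader might also infer that a death could not be told apart from other loss when a month-24 CDR-SB is missing. Section 9.5.5 (earlier text) provides for contacting subjects who cease to return, by mail, phone or other means, to learn the reason and whether adverse events occurred. Some deaths would be found that way, so the inference fails.

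Two further objections stand in part. Adverse events having been listed at these visits in earlier text is superseded wording and not in itself an error; it shows only that collection there was once planned. A 4-week window also matches the visible definition of a treatment-emergent event and is reasonable for non-serious events.

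What the objections do not remove is that unrelated events after week 4 have no stated collection to month 24 and, if the 12-week window applies, neither do unrelated SAEs. The open-ended rule for related SAEs does not fill this gap. A comparison by arm needs all serious events, because individual causality judgements made long after dosing are the weakest filter to rely on.

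**Conclusion.** The asymmetry is real and stems from a stated rule of Version 7.0: benefit is followed to month 24 by randomised arm, while new non-procedural harm in discontinuers is followed to 4 weeks after the last dose. On the assumed 5% to 30% who stop and stay, with uniform stopping times, 2.3% to 13.9% of planned subject-months have no new-event collection. If the 12-week SAE window still holds, 2.0% to 11.7% have none for unrelated SAEs. The upper ends borrow a dropout allowance that describes a different group, so they should be read as bounds and not as estimates. Any imbalance between arms is a risk and is not documented.

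The change is worth making because it is cheap and removes a possible bias from the safety comparison. Whether the SAE and death part is already dealt with in the Version 7.0 body cannot be settled from the text supplied.

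**What to change.** 1. In the Core Study part of the synopsis, where early discontinuation is described, add: vital status and SAEs will be recorded at the 12- and 24-month return visits for all subjects who remain on study, whatever the time since last dose.
2. State the SAE and death window explicitly in the synopsis and reconcile it with Sections 9.3.3, 9.5.1.5.1 and 9.5.4.1 of the body.
3. Summarise deaths and SAEs to month 24 by randomised arm in treated subjects, in tables separate from those for treatment-emergent events.
4. Keep the 4-week limit for non-serious events if wished.

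The cost is a few eCRF entries and some additional SAE reports, with no new visit or procedure. The drawback is that attribution is weaker for events long after dosing, which is why they belong in their own tables.
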